Renal Failure (Acute): Acute post-operative renal insufficiency resulting in one or more of the following: (a) increase of > 1.0 mg/dl in serum creatinine from most recent prior measured level, and current measured absolute value is > 2.0 mg/dl; (b) a new requirement for dialysis.

Renal Insufficiency: An increase in serum creatinine of ≥ 1.0 mg/dl over previous value requiring medical treatment but which does not require dialysis to resolve.

Respiratory Failure: New onset of respiratory insufficiency that requires placement of endotracheal tube and/or pneumothorax with or without chest tube.

Respiratory Insufficiency: Deterioration of subject's respiratory efforts that require supportive or medical treatment.

Restenosis: Reoccurrence of narrowing or blockage or target lesion. Recurrence of $\geq 50\%$ diameter stenosis within 1 cm proximal and/or distal to the target lesion as measured by duplex ultrasound (PSV ≥ 2.5) or angiography (note: in cases where both imaging modalities are available, the angiography will take precedence).

Retroperitoneal Bleed: Bleeding into the back of the abdomen from a vascular access or puncture site.

Rutherford Clinical Category Scale: Clinical scale identifying three grades of claudication and three grades of critical limb ischemia ranging from rest pain alone to minor and major tissue loss.

Category	Clinical Description
0	Asymptomatic

1	Mild claudication
2	Moderate claudication
3	Severe claudication
4	Ischemic rest pain
5	Minor tissue loss
6	Ulceration or gangrene

Stent Fracture: Defined as clear interruption of stent strut observed in a minimum of two projections, determined by core lab examination of X-ray images.

Stent Strut Fracture Types:

Type 0: No strut fractures.

Type I: Single strut fracture only.

Type II: Multiple single strut fractures that can occur at different sites.

Type III: Multiple strut fractures resulting in complete transection of the stent, without displacement of the stent segments.

Type IV: Multiple strut fractures resulting in displacement of segments of the stent.

Type V: Spiral strut fracture.

Stroke: Any neurological deficit defined as an acute episode of focal or global neurological dysfunction caused by brain, spinal cord, or retinal vascular injury as a result of hemorrhage or infarction. May be further categorized as:

Ischemic Stroke: defined as an acute episode of focal cerebral, spinal, or retinal dysfunction caused by infarction of central nervous system tissue.

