4.8 ENROLLMENT

According to ISO 14155:2011, enrollment in the study occurs at the time of informed consent; however, for the purposes of this study, only subjects who are consented and meet all the study inclusion criteria and none of the study exclusion criteria, venous and arterial access has been achieved and study device advanced beyond the sheath will be considered enrolled into the study. Therefore, the enrollment date (Day 0) will be the date of the study index procedure; the enrollment date will not be the date of informed consent for this study. Subjects in whom the PQ Bypass System is inserted into the vascular and/or the procedure was aborted without treatment with the device shall be followed through discharge for safety only and allowed to exit the study.

Investigators will access the target artery and the corresponding ipsilateral vein using standard percutaneous techniques and devices. Patient eligibility will be confirmed prior to insertion of the study device, based on procedural angiogram and sheath placement.

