4.9.3 Vascular Access and Guidewire Delivery

Investigators will access the target lesion and the corresponding ipsilateral vein using standard percutaneous techniques and devices. Patient eligibility will be confirmed prior to insertion of the study device, based on procedural imaging and sheath placement.

After eligibility confirmation, the PQ Crossing Device and the PQ Snare will be used to deliver a guidewire from the arterial segment proximal to the target lesion, through the femoral vein and back into the reconstituted artery distal to the target lesion. The number of deployment attempts for guidewire placement access at each anastomosis will be recorded.

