7.2.2. Intention to Treat (ITT)

The ITT Cohort includes all subjects enrolled in the IDE Study. The ITT Cohort will be the primary analysis population to determine if the primary safety endpoint was met in the study.

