Type E: Persistent luminal filling defect with delayed run-off of the contrast material in the distal lumen.

Type F: Filling defect accompanied by total coronary occlusion.

Embolization, Distal: Any distal emboli confirmed by imaging.

Embolization, Symptomatic: Clinical signs or symptoms of distal emboli detected in the treated limb distal to the treated lesion after the index procedure **or** noted angiographically and requiring mechanical or pharmacologic means to improve flow. This includes new abrupt occlusions or filling defects.

Enrollment: Subjects who are consented and meet all the study inclusion criteria and none of the study exclusion criteria and are treated or treatment is attempted with the study device will be considered enrolled into the study. Subjects who do not meet all inclusion and exclusion criteria (e.g., including ability to cross the lesion with a guidewire, target reference vessel diameter, patent tibioperoneal artery in the target limb, etc.) will be considered an angiographic screen failure and will not be followed in the study (no data will be collected on these subjects).

Hematoma: Collection of blood (or its degradation products) that exceeds 8 cm in diameter, requires treatment, or prolongs hospitalization.

Hypertension: Systolic BP >140 mmHg, or diastolic >90 mmHg requiring specific medical therapy.

Hypotension: Any prolonged systolic blood pressure <80 mmHg associated with symptoms and requiring intravenous vasopressor medications.

Infection, access site: Infection at the vascular access site, documented by lab culture or clinical evidence requiring medical treatment (irrigation, debridement, antibiotics, etc.) to resolve.

Infection, systemic: Systemic infection documented by positive lab culture or clinical evidence, requiring medical treatment to treat and resolve.

Intention to Treat (ITT): The principle of including outcomes of all subjects in the analysis who are enrolled and treated (attempted or completed) into the study, regardless of noncompliance, Protocol deviations, or withdrawal.

Limb Ischemia: Deficient supply of oxygenated blood to the tissues in the limbs that is due to obstruction of the inflow of arterial blood characterized by pain and/or discoloration of the limb and/or tissue loss.

Luminal Patency: Restenosis <50% as determined by angiography or duplex ultrasound.

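### The enrollment and ITT definitions conflict, so a failed guidewire delivery or a later-found eligibility violation could be read out of the primary safety population

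*Combined protocol and SAP*

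**What the plan says.** **Section 15, Enrollment.** The entry's first sentence enrols eligible subjects who "are treated or treatment is attempted with the study device will be considered enrolled into the study". Its second sentence says that a subject who does not meet all criteria, with "including ability to cross the lesion with a guidewire" among the examples, "will be considered an angiographic screen failure and will not be followed in the study (no data will be collected on these subjects").

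**Section 4.8.** Enrollment requires that all criteria are met and that "venous and arterial access has been achieved and study device advanced beyond the sheath will be considered enrolled into the study". Eligibility is to be confirmed before the study device is inserted. Subjects whose procedure is aborted after insertion "shall be followed through discharge for safety only and allowed to exit the study".

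**Section 4.9.3.** After eligibility is confirmed, "the PQ Crossing Device and the PQ Snare will be used to deliver a guidewire" from the artery above the lesion, through the femoral vein, and back into the artery below it.

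**Section 7.2.2.** "The ITT Cohort includes all subjects enrolled in the IDE Study", and this cohort is the primary population for the safety endpoint. The Section 15 ITT entry covers attempted as well as completed treatment and applies regardless of protocol deviations.

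**Section 7.2.4.** Eligibility violations are removed from the Per Protocol set, which is a subset of MITT.

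**Sections 3.1 and 3.2.** Neither lists guidewire crossing. The nearest item is inclusion criterion 10, access to the SFA origin.

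**The concern.** In a single-arm trial against a fixed performance goal, the denominator should not depend on how the procedure went. Two readings of the current text let it do so.

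1. Guidewire placement is the stated intended use of the PQ Crossing Device (Section 1.4). A site whose guidewire delivery fails can find wording in Section 15 that calls this an unmet eligibility item and directs that no data be collected.
2. Both enrollment definitions require every criterion to be met. A subject treated and later found ineligible was then, literally, never enrolled, and so is outside ITT. Such findings are foreseeable: lesion length and vessel diameter are judged visually by the investigator (Section 3.1), and the core labs then analyze the images against the eligibility criteria (Section 9.12).

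At stake are the 30-day freedom-from-MAE rate, which is a tested primary endpoint, and technical success, which is a descriptive secondary endpoint.

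**Working it through.** **Inputs from the plan.** Section 7.1.2: safety goal 84%, assumed rate 92%, one-sided alpha 0.025, exact method, 169 evaluable for 88% power, and a success count of 163 at 181 evaluable. Section 4.3: 202 subjects. Section 1.5: 98.8% technical success in DETOUR I.

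**Formulas.** The passing count r is the smallest value with P(X ≥ r | n, 0.84) ≤ 0.025. Power is P(X ≥ r | n, 0.92). The lower limit for x of n is the Clopper-Pearson limit, the 0.025 quantile of Beta(x, n − x + 1).

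**Plan's own figures.** At n = 169, r = 152, with attained alpha 0.0183 and power 86.9%. This is close to the stated 88%. At n = 181, the smallest passing count is 162 (89.5%, lower limit 84.09%). The plan's count of 163 is one higher, and its 89.6% matches 163/182 = 89.56%. I use 162.

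**Near the margin.** Suppose the full device-exposed set just fails, and MAE cases are then left out:

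| Free of MAE / analysed | Lower limit | Against 84% |
|---|---|---|
| 161/181 | 83.45% | fails |
| 161/180 (one MAE case omitted) | 84.01% | passes |
| 161/179 (two omitted) | 84.57% | passes |
| 180/202 | 83.98% | fails |
| 180/201 (one omitted) | 84.47% | passes |

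**At the planned rate.** 0.92 × 181 = 166.5, so take 167/181 as the analysed result, with lower limit 87.36%. Put omitted MAE cases back:
- five: 167/186, 84.51%, still passes;
- six: 167/187, 83.97%, fails.

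**Effect on type I error.** Let the true rate over all device-exposed subjects be exactly 84%. A fraction f is excluded, with MAE rate q. The rate among those kept is (0.84 − f(1 − q)) / (1 − f). The chance of at least 162 of 181, which is 0.023 with no exclusion, becomes:

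| f | q = 8% | q = 30% | q = 50% |
|---|---|---|---|
| 1.2% | 0.021 | 0.027 | 0.032 |
| 2% | 0.020 | 0.029 | 0.040 |
| 5% | 0.016 | 0.042 | 0.089 |

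The documents give neither f nor q, so every cell rests on assumption. For scale, 1.2% is the complement of DETOUR I's 98.8% technical success, and 202 × 0.012 = 2.4 subjects. Not all of those need be guidewire failures.

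**Aborted cases.** Section 4.8 lets them exit at discharge. Section 7.3.1 counts a subject for safety only with at least 23 days of follow-up or an event. An aborted case with no event by discharge is therefore in ITT but not evaluable, and a later MAE can go unseen. If two such event-free subjects drop from 162/181, the result is 160/179, lower limit 83.92%. That loss works against the device; an unseen MAE works for it.

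**The case against.** The case that the plan already keeps these subjects is substantial.

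- **Wording.** The phrase concerns crossing the lesion. The device wire goes around the lesion through the vein, so failing to cross is not literally a failure of the device. The other examples in the entry are anatomical, which fits conventional wiring before device use.
- **Timing.** Eligibility is settled before insertion, and an angiographic screen failure is naturally a pre-device category.
- **Attempted cases.** The Section 15 enrollment and ITT entries both cover attempted treatment, and Section 4.8 enrols at passage beyond the sheath.
- **Ineligible subjects.** Section 9.6 classes eligibility departures as major deviations. Section 7.2.4 removes them from a subset of MITT, which makes sense only if they were in ITT to begin with.
- **Size.** A result of 161/181 is a chosen knife-edge. Perforation alone is not an MAE, and bleeding counts only with transfusion or surgery.

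All of this stands. A reader might infer that the plan excludes device failures from ITT, or that the safety rate is necessarily biased upward. The documents support neither: the weight of the text favours inclusion, and with an MAE rate of about 8% among those excluded, exclusion is slightly conservative.

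These points do not remove the conflict. If Section 4.8 governs, the Section 15 example is wrong. If the example means wiring before device use, it is still a criterion missing from Section 3. The enrollment definitions still condition on full eligibility while the ITT entry disregards deviations, and no rule of precedence is stated.

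**Conclusion.** The point holds as a conflict between definitions that decides who is in the primary safety population. The text permits a device-exposed subject to be reclassified out of ITT; it does not establish that this will happen. One omitted MAE case can reverse a result at the margin, but about six are needed at the planned 92%. The direction of any bias depends on the MAE rate among excluded subjects, which the documents do not give: upward if they fare worse than those kept, negligible or conservative otherwise. The change is worth making because it is nearly free and closes a route to post-hoc exclusion in an open, single-arm trial.

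**What to change.** 1. **Section 15, Enrollment.** Delete the guidewire example and refer the entry to Section 4.8. Limit screen failure to subjects in whom no PQ device was advanced beyond the sheath. If conventional wiring before device use is a real requirement, it belongs in Section 3.1.
2. **Sections 4.8 and 7.2.2.** State that ITT is every non-roll-in subject in whom any PQ device was advanced beyond the sheath, regardless of procedural outcome or of an eligibility violation found later.
3. **Sections 4.8 and 7.3.1.** Reconcile the discharge-only follow-up of aborted cases with the 23-day safety denominator, and say how an aborted case without an event is counted. Rewording ITT alone does not make these subjects evaluable.

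Items 1 and 2 are a few sentences and add no data collection beyond what Section 4.8 already requires. A few more unfavourable outcomes may be counted. Item 3 costs only wording if it settles how the cases are counted; obtaining 30-day status for aborted cases would add a small follow-up burden.
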